9.7 Data Analysis

9.7.1 Datasets and Analysis Cohorts

The effectiveness analysis will be carried out on the primary and secondary endpoints of the study for the following treatment regimens:

- Standard prophylaxis
- On-demand treatment
- Episodic prophylaxis
- ITI

Effectiveness of switch from on-demand to prophylaxis dataset (ESODTP)

Evaluation of effectiveness (ABR, AJBR) after switch from on-demand regimen to prophylaxis in moderate moderately severe and severe hemophilia B patients.

Safety Analysis Set (SAS)

The SAS will consist of data for all subjects who were enrolled, met all inclusion and none of the exclusion criteria, and received at least 1 infusion of FIX (RIXUBIS). If 2 or more AEs are reported together as a unit, the individual Medical Dictionary for Regulatory Activities (MedDRA) preferred terms will be counted as separate events.

Effectiveness Full Analysis Set (EFAS)

The EFAS will consist of data from all subjects who were enrolled, met all inclusion and none of the exclusion criteria. This dataset will be used for the primary effectiveness analysis for the comparison of annualized bleeding rates (ABR, AJBR) between each independent treatment regimen (i.e., prophylaxis, on-demand).

Calculation of Annualized Bleeding Rates (ABR) and monthly Bleeding Rate (MBR)

The ABR will be calculated as follows: $(\text{total number of bleeding episodes} \div \text{observed treatment period in days}) * 365.25$. The monthly bleeding rates (MBR) will be calculated as follows: $(\text{total number of bleeding episodes} \div \text{observed treatment period in days}) * 30.5$. The treatment period for surgeries will be excluded from the bleed rate calculation.

Bleeding occurring prior to the first prophylactic infusion will not be included in the estimation of bleeding rate. The observation period for the on-demand regimen will commence on the day of enrollment (met all inclusion and none of the exclusion criteria); the period for prophylaxis will commence at the first prophylactic infusion once enrolled (met all inclusion and none of the exclusion criteria).

Minimal Observed Treatment Period to Estimate ABR

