For enrolled subjects that have met all inclusion and none of the exclusion criteria, subjects who have at least 1 assessment [defined as having a minimum of 3-month (≥ 90 days) observational period on regimen] but do not complete the full study period of four years, the ABR will be estimated from the interval assessments. For subjects who do not have at least 1 interval assessment, the median rate observed for the assigned regimen will be substituted.

Health Related Quality of Life Analysis Set (HRQoLAS)

The HRQoLAS will consist of all subjects who have been enrolled and met all inclusion and none of the exclusion criteria and who have provided any available assessments at any available study visit.

Pharmacoeconomics Analysis Set (PEAS)

The PEAS will consist of all the subjects that have been enrolled, met all inclusion and none of the exclusion criteria and have provided any available assessments at any available study visit.

Joint Health/Function Analysis Set (JHFAS)

The JHFAS will consist of all subjects who have been enrolled, met all inclusion and none of the exclusion criteria and have provided any available assessments at any available study visit.

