9.7.3 Methods of Analysis

Descriptive statistics of all endpoints will include specifically but not exclusively, arithmetic mean, medians, standard deviations, minimum, maximum, proportions, frequency counts, 25th and 75th percentiles, and 95% confidence intervals of select point estimates. Figures will be prepared to illustrate the patterns of data over time where appropriate. The number of subjects included in each analysis set will be reported.

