9.7.3.2 Methods of Analysis for Effectiveness Endpoints

The method of analysis will be applied to the effectiveness endpoint. The primary endpoint, ABR of all types of bleeding episodes, will be calculated for each subject and described for prophylaxis.

In addition, separate description of ABR will be provided for each of the following treatment regimens, assuming a minimum observed period of (≥ 90 days) is fulfilled:

- Standard prophylaxis
- On-demand treatment
- Episodic prophylaxis
- ITI

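### Giving subjects with under 90 days the regimen's median ABR lowers the mean, shrinks the spread, and conflicts with the protocol's own rules on short follow-up and withdrawal

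*Protocol*

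**What the plan says.** All references are to the protocol.

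- **Endpoint (Section 9.7.3.2).** "The primary endpoint, ABR of all types of bleeding episodes, will be calculated for each subject and described for prophylaxis".
- **Analysis set (Section 9.7.1).** "The EFAS will consist of data from all subjects who were enrolled, met all inclusion and none of the exclusion criteria". There is no minimum follow-up. On its use: "This dataset will be used for the primary effectiveness analysis for the comparison of annualized bleeding rates (ABR, AJBR) between each independent treatment regimen".
- **Short follow-up (Section 9.7.1).** An assessment is "defined as having a minimum of 3-month (≥ 90 days) observational period on regimen". Without one: "For subjects who do not have at least 1 interval assessment, the median rate observed for the assigned regimen will be substituted". The text provides no flag, sensitivity analysis or variance adjustment for the substituted values.
- **Short follow-up again (Section 9.7.3.2).** ABR is described separately for standard prophylaxis, on-demand treatment, episodic prophylaxis and immune tolerance induction, "assuming a minimum observed period of (≥ 90 days) is fulfilled". Section 9.7.3.4.1 sets a similar condition for on-demand ABR.
- **Withdrawal and discontinuation (Sections 9.2.7 and 9.3.7).** Data collected up to that point are to be used in the analysis.
- **Summaries (Section 9.7.3).** For all endpoints: "arithmetic mean, medians, standard deviations, minimum, maximum, proportions, frequency counts, 25th and 75th percentiles", and also "95% confidence intervals of select point estimates", without saying which. Section 4 (Abstract), Section 9.1 and Section 9.5 say that no interval estimation will be applied.

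**The concern.** The rule fills a gap in the primary endpoint with one constant per regimen. This has three consequences.

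First, ABR is skewed to the right, so the median lies below the mean. Each copy of the median added to the data pulls the mean down and therefore makes prophylaxis look somewhat better.

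Second, the copies sit in the middle of the distribution and count as full observations. SD and interquartile range shrink while n grows, so the summary looks more precise as more data are missing.

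Third, a subject who bled several times in 80 days is entered as a typical subject, although those bleeds and days were recorded and other sections say that they will be used.

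The protocol also does not settle whether a subject with short follow-up is excluded from the ABR description or imputed in it.

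**Working it through.** **The plan's own figures.** The protocol gives no expected share of subjects under 90 days, no precision target and no dropout rate. Its size of about 80 evaluable subjects is stated not to rest on statistical considerations. There is thus no planned figure to reproduce, and the share substituted has to be assumed.

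**Inputs.** Mean m = 2.7, SD s = 3.14 and median d = 2.0, from the paediatric prophylaxis study in Section 7.2. N = 80 (Section 9.5). Share substituted f = 5, 10 or 20% (assumption), so k = 4, 8 or 16 subjects are substituted and n = N − k are observed.

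**Formulas.**

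- Mean after substitution: M = (n·m + k·d)/N.
- SD after substitution: S = √{[(n−1)s² + n(m−M)² + k(d−M)²]/(N−1)}.
- 95% half-width from observed subjects: t(n−1)·s/√n. With substituted values counted as data: t(N−1)·S/√N.

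**Worked case, f = 10%.** M = (72 × 2.7 + 8 × 2.0)/80 = 210.4/80 = 2.63. S² = (71 × 9.8596 + 72 × 0.07² + 8 × 0.63²)/79 = (700.03 + 0.35 + 3.18)/79 = 8.906, so S = 2.984.

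| Share substituted | Mean (change) | SD (change) | Half-width, observed only | Half-width, substituted | Ratio |
|---|---|---|---|---|---|
| 5% | 2.665 (−1.3%) | 3.063 (−2.4%) | 0.718 | 0.682 | 0.950 |
| 10% | 2.630 (−2.6%) | 2.984 (−5.0%) | 0.738 | 0.664 | 0.900 |
| 20% | 2.560 (−5.2%) | 2.818 (−10.2%) | 0.784 | 0.627 | 0.800 |

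The prophylaxis group will be smaller than 80. At N = 40 the relative changes are almost the same (ratios 0.949, 0.898 and 0.795).

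**Median.** Adding copies of the observed median leaves the sample median where it was.

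**Interquartile range and coverage.** These come from a simulation (gamma-distributed ABR, mean 2.7, SD 3.14, N = 80, 6,000 runs). With short follow-up unrelated to bleeding, the interquartile range falls from about 3.13 to 2.93, 2.71 and 2.23 at 5, 10 and 20%. Coverage of a nominal 95% interval for the mean is 91, 89 and 81%, against about 94% from observed subjects only. If subjects above the median are twice as likely to have short follow-up, coverage is 90, 86 and 68% with substitution and 92, 92 and 88% without. Excluding these subjects therefore does not remove selection bias. The gamma's median is 1.62, not 2.0, so the fall in mean is taken from the table, not from the simulation.

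**The sections side by side.** Section 9.7.1 imputes below 90 days; Section 9.7.3.2 describes regimen ABR, including standard prophylaxis, only from 90 days. Sections 9.2.7 and 9.3.7 keep data up to withdrawal or discontinuation; Section 9.7.1 replaces them in the ABR. Section 14.3 limits episodic prophylaxis to 3 months, so hardly any such period can reach 90 days, and the median to substitute for that regimen may hardly exist.

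**The case against.** The case for a milder view has four parts.

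- **Few subjects may be affected.** Follow-up is planned for 4 years (Section 9.2.2). Section 14.3 defines short-term prophylaxis as lasting more than 3 months, so a regimen that itself ends earlier counts as episodic. What remains is established prophylaxis with under 90 observed days. This stands: the share is unknown and at 5% the effect is small. It could be larger at the yearly interim analyses (Section 9.7.4). With uniform accrual and the same rule at interims, both assumptions, those enrolled in the last 90 days would be 90/365 = 25% at month 12 and 90/730 = 12% at month 24.
- **Section 9.7.3.2 may switch the rule off.** If its 90-day condition governs every ABR table, no substituted value appears. But the condition is attached to the additional description by regimen, not to the sentence on the primary endpoint. At best, prophylaxis ABR would be reported twice under different rules.
- **Confidence intervals may not be reported for ABR.** This stands. Section 9.7.3 does not name the estimates that get one, and three other places deny interval estimation. The loss of width and coverage is therefore conditional.
- **Nothing is tested.** The study is descriptive, and no decision rule on ABR depends on the substituted values. This stands and bears on severity.

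A reader might infer more than the protocol supports. That the primary endpoint as a whole is biased does not follow: mean and median are both planned, neither is ranked first, and the substitution leaves the median alone. That early leavers are frequent bleeders is not stated anywhere. A reader might also want at least one infusion as a condition for the effectiveness set, since a never-infused subject could receive a rate. For on-demand subjects that would do harm: their period starts at enrolment, one who never bleeds needs no infusion, and dropping such true zeros would raise the on-demand ABR.

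**Conclusion.** The point holds in limited form. Section 9.7.1 enters a constant as if it were an observed ABR. With the skewness shown in Section 7.2, this lowers the mean by 1.3, 2.6 or 5.2% and the SD by about 2, 5 or 10% for an assumed 5, 10 or 20% substituted, and it shrinks the interquartile range. Any 95% confidence interval for the mean would be about 5, 10 or 20% too narrow. The sizes rest on the assumed share and on this cohort resembling the paediatric study. The conflicts with Sections 9.7.3.2, 9.2.7 and 9.3.7 hold at any share. Severity: should-fix.

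**What to change.** 1. Delete the substitution sentence in Section 9.7.1 and reconcile that section with Section 9.7.3.2, so that one 90-day rule governs every ABR summary.
2. Summarise subject-level ABR for subjects with at least 90 days on regimen, and report per regimen how many were left out.
3. Add a rate per regimen that uses every subject's actual bleeds and observed days, whatever their length: total bleeds divided by total person-time, or a negative binomial model with log days as offset. This honours Sections 9.2.7 and 9.3.7 and shows whether leaving out short follow-up matters. Pooled person-time gives long follow-up more weight than a mean of subject rates does, so label the two separately.
4. State whether mean ABR gets a confidence interval, and align Section 9.7.3 with Sections 4, 9.1 and 9.5.
5. Do not add an infusion requirement to the effectiveness set for on-demand subjects.

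The cost is a few sentences and one standard calculation, slightly fewer subjects with an individual ABR, and a slightly wider reported spread. No extra data are needed.

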9.7.2 Handling of Missing, Unused, and Spurious Data

If a subject's current weight is missing, the subject's last recorded weight will be used to calculate the weight-adjusted dose (IU/kg).

9.7.3 Methods of Analysis

Descriptive statistics of all endpoints will include specifically but not exclusively, arithmetic mean, medians, standard deviations, minimum, maximum, proportions, frequency counts, 25th and 75th percentiles, and 95% confidence intervals of select point estimates. Figures will be prepared to illustrate the patterns of data over time where appropriate. The number of subjects included in each analysis set will be reported.

9.7.3.1 Primary Endpoint

(See Section [9.3.1](#))

To describe hemostatic effectiveness in the prevention of bleeding events in subjects with hemophilia B receiving rFIX (RIXUBIS) in routine clinical practice.

9.7.3.2 Methods of Analysis for Effectiveness Endpoints

The method of analysis will be applied to the effectiveness endpoint. The primary endpoint, ABR of all types of bleeding episodes, will be calculated for each subject and described for prophylaxis.

In addition, separate description of ABR will be provided for each of the following treatment regimens, assuming a minimum observed period of (≥ 90 days) is fulfilled:

- Standard prophylaxis
- On-demand treatment
- Episodic prophylaxis
- ITI

9.7.3.3 Methods of Analysis for Effectiveness Criteria

The annualized rate of bleeding episodes in joints, target joints, and other anatomical locations for the two independent samples (on-demand or prophylaxis) will be summarized. The frequency distribution for the number of infusions for bleed treatment will be reported for each of the on-demand and prophylaxis treatment regimens. The median number of infusions per bleeding episode for each subject will be calculated and the median for subjects in each treatment regimen will be compared using the Mann-Whitney (Wilcoxon-Rank Sum) test. The total weight-adjusted dose (IU/kg) per bleeding episode per subject will be described for both the on-demand and prophylaxis treatment regimens and will be compared using the Mann-Whitney (Wilcoxon-Rank Sum) test.

Corresponding to all treated FIX (RIXUBIS) bleeding episodes, the following parameters will be computed separately by treatment regimen (prophylaxis, on-demand):

Total number of subjects infused
Total bleed exposure days
Total number of bleed treatment infusions
Units administered per subject, per infusion (IU)
Units administered per subject, per bleed (IU)
Annualized units administered for bleed treatment, per subject (IU)
Total units administered for bleed treatment, per subject (IU)
Weight-adjusted dose per subject, per bleed (IU/kg)
Weight-adjusted dose per subject, per infusion (IU/kg)
Annualized weight-adjusted dose for bleed treatment, per subject (IU/kg)
Total weight-adjusted dose for bleed treatment, per subject (IU/kg)

Assessment of effectiveness:

Corresponding to subjects given prophylactic infusions (RIXUBIS) in this study, the following parameters will be computed by treatment regimen (prophylaxis, on-demand):

Total number of subjects infused
Total exposure days
Total number of infusions
Number of unique lots used
Units administered per subject, per infusion (IU)
Units administered per subject, per week (IU)
Units administered per subject, per month (IU)
Annualized units administered, per subject (IU)
Total units administered, per subject (IU)
Weight-adjusted dose per subject, per infusion (IU/kg)
Weight-adjusted dose per subject, per week (IU/kg)
Weight-adjusted dose per subject, per month (IU/kg)
Annualized weight-adjusted dose, per subject (IU/kg)
Total weight-adjusted dose, per subject (IU/kg)

The occurrence of new target joints and bleeding episodes used to assess new target joints will be summarized by treatment regimen.

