Pharmacokinetics, safety and efficacy has been shown in a phase I/III clinical study in previously treated patients (PTPs) with severe (<1% FIX) and moderately severe ($\leq 2\%$ FIX level).^{1,3} RIXUBIS was safe and well tolerated in all 73 patients in the full analysis set. AEs considered related to treatment (2.7% incidence) were mild and transient. No hypersensitivity reaction, inhibitor formation or thrombotic events were observed. PK equivalence of RIXUBIS in comparison to an already licenced recombinant FIX was evaluated by comparing the ratio of the geometric mean of the area under the curve (AUC) per dose over the 0-72h period. Twice weekly prophylaxis (mean 49.5 IU/kg/dose) was effective in preventing bleeding episodes with a significantly lower (by 79%) annualized bleeding rate (ABR) compared to a historical group treated on-demand (4.2 Vs 20.0). Of the subjects on prophylaxis, 43% (24/56) did not bleed throughout the duration of the study. Of 249 acute bleeds, 211 (84.7%) were controlled with 1 or 2 infusions of RIXUBIS. Hemostatic effectiveness was rated excellent or good in 96% of all treated bleeding episodes. The results of this study indicate that RIXUBIS treatment is safe and efficacious in treating bleeds and as routine prophylaxis in patients aged 12 years and older with hemophilia B^{2,3}.

Additionally, this clinical trial assessed aspects of quality of life (QoL) of hemophilia B patients². Health-related QoL (HRQoL) burden of hemophilia B, the benefit of RIXUBIS prophylaxis and the HRQoL benefits of achieving a zero annual bleed rate was investigated. Short-Form Health Survey (SF-36) scores showed statistically significant and clinically meaningful improvements in overall physical HRQoL measured by the Physical Component Summary (PCS) score, Bodily Pain (BP) and Role Physical (RP) domains. Subjects that switched to prophylaxis from intermittent prophylaxis or on-demand treatment experienced more pronounced improvements not only in PCS, BP and RP scores, but also in Vitality (VT), Social Functioning (SF) and General Health (GH) domains. Subjects achieving zero bleeds reported reduced BP scores. Therefore prophylaxis with RIXUBIS improved HRQoL in patients with moderately severe and severe hemophilia B by reducing bleeds.

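### The rank-sum test on per-subject median infusions per bleed responds to how often subjects bleed, so a small p-value would not show that bleeds on one regimen need more infusions

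*Protocol*

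**What the plan says.** Section 9.7.3.3 of the protocol reduces each subject to a single number: "The median number of infusions per bleeding episode for each subject will be calculated and the median for subjects in each treatment regimen will be" tested against each other by Mann-Whitney (Wilcoxon rank-sum). It sets no weighting, no minimum number of bleeds and no bleed-level model. The preceding sentence plans a frequency distribution of infusions per bleed by regimen. The next sentence takes up dose: "The total weight-adjusted dose (IU/kg) per bleeding episode per subject will be described for both the on-demand and prophylaxis treatment regimens", which also "will be compared using the Mann-Whitney (Wilcoxon-Rank Sum) test". The section calls the regimens independent samples: "for the two independent samples (on-demand or prophylaxis) will be summarized".

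The background in Section 7.2 gives an ABR on prophylaxis "compared to a historical group treated on-demand (4.2 Vs 20.0"), and reports: "Of 249 acute bleeds, 211 (84.7%) were controlled with 1 or 2 infusions of RIXUBIS". It does not split one infusion from two.

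Sections 4 (study size), 9.1 and 9.5 say that no hypothesis testing will be applied.

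**The concern.** A sample median is more variable when it rests on few observations. Infusions per bleed is a small integer, so that variability decides whether a subject's median is 1, 1.5, 2 or more. Subjects with many bleeds have medians that settle on the population value. Subjects with few bleeds scatter. If one regimen has many bleeds per subject and the other few, the two sets of medians differ in distribution with no difference between the bleeds themselves.

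The rank-sum test is valid for equality of the distributions of subject medians. But that null is generally false once bleed frequency differs, and bleed frequency is what prophylaxis is meant to change. At stake is the reading of a secondary result, the number of infusions needed to resolve a bleed (Section 9.3.2.1).

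**Working it through.** **No plan figure to reproduce.** The protocol gives no alpha, power or effect size for this test. Its background figures do reproduce: 1 - 4.2/20.0 = 79%, and 211/249 = 84.7%.

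**Inputs from the protocol**
- ABR 4.2 and 20.0, ratio 20.0/4.2 = 4.8 (Section 7.2).
- Follow-up 4 years (Section 9.2.2), so 4.2 x 4 = 16.8 and 20.0 x 4 = 80 expected bleeds per subject.
- P(1 or 2 infusions) = 0.847 (Section 7.2).
- About 80 subjects (Section 9.5).

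**Assumptions, not in the protocol**
- Two-sided 5% level.
- Groups of 60/20 or 40/40 (prophylaxis/on demand).
- P(1 infusion), called p, between 0.35 and 0.70.
- Overdispersed bleed counts.
- Between-subject variation in infusions per bleed, expressed as an ICC.

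**Step 1, exact.** Give every bleed in both regimens the same distribution. For an odd number n of bleeds, the subject's median exceeds 1 unless at least (n+1)/2 bleeds needed one infusion:

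P(median > 1) = 1 - sum over k from (n+1)/2 to n of C(n,k) p^k (1-p)^(n-k)

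For n = 3 and p = 0.65: 1 - (3 x 0.65² x 0.35 + 0.65³) = 1 - 0.718 = 0.28.

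| p | n=1 | n=3 | n=5 | n=17 | n=81 |
|---|---|---|---|---|---|
| 0.65 | 35% | 28% | 24% | 10% | 0.3% |
| 0.60 | 40% | 35% | 32% | 20% | 3% |
| 0.50 | 50% | 50% | 50% | 50% | 50% |
| 0.40 | 60% | 65% | 68% | 80% | 97% |

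Above p = 0.5, subjects with few bleeds more often have a median over 1, so prophylaxis looks worse. Below 0.5 the order reverses and prophylaxis looks better.

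**Step 2, the planned test with identical bleeds in both regimens.** Bleed counts are Poisson-gamma (dispersion 1.0 on prophylaxis, 0.3 on demand), p = 0.65, 4 years. Subjects without bleeds have no median and are left out.

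| ICC | planned test, 60/20 | planned test, 40/40 | bleed-level clustered, 60/20 and 40/40 |
|---|---|---|---|
| 0 | 50% | 77% | 5%, 5% |
| 0.05 | 15% | 29% | 6%, 7% |
| 0.1 | 10% | 15% | 7%, 7% |

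At ICC 0.2 the planned test rejects about 5-10%.

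**Step 3, dependence on p, with no between-subject variation.** Negative binomial counts (shape 0.6 and 2.0), 4 years.

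| p | 0.35 | 0.45 | 0.50 | 0.55 | 0.60 | 0.65 | 0.70 |
|---|---|---|---|---|---|---|---|
| 40/40 | 38% | 23% | 5.5% | 35% | 64% | 68% | 60% |
| 60/20 | 12% | 15% | 5% | 26% | 40% | 41% | 19% |

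With Dirichlet totals of 20 and 5 (ICC 1/21 = 0.05 and 1/6 = 0.17), the 40/40 figures for p of 0.40 to 0.65 fall to 9-26% and 6-10%.

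**Control.** With equal bleed rates in both groups (40/40, 4 years), the planned test rejects 4-6%. The unequal bleed frequency therefore causes the excess.

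**The case against.** **The large figures need favourable assumptions.** This stands. Rejection of 50-80% requires that no subject differs from another in infusions per bleed. That is unlikely where the physician chooses the regimen (Section 9.1) and Section 9.9 itself expects wide differences in treatment approach and dosing. A separate set of runs at 60/20 with ICC 0.1-0.3 and p of 0.42-0.65 gave only 3-6.5%. The ABR of 20.0 is also borrowed: it comes from a historical group set against a trial in FIX levels up to 2%, while this study admits levels up to 5%. At an on-demand ABR of 8-10 and ICC 0.1-0.3, rejection was about 3-10%.

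**The study is descriptive.** Partly stands. No decision rests on this p-value, but Section 9.7.3.3 still prescribes it.

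**Three stronger readings are tempting and unsupported.**
- *Prophylaxis will falsely look worse.* The direction turns on the split between one and two infusions, which the protocol does not give.
- *The plan would miss a difference in hard-to-control bleeds.* The frequency distribution by regimen already shows the share needing three or more infusions, and per-bleed effectiveness ratings are planned (Section 9.7.3.4.1). A median is blind only to a shift confined to two versus three or more. For a shift across all categories (70/20/10% against 45/30/25%), the planned test had 84-99% power at 60/20 and ICC 0.05-0.2.
- *The dose comparison fails in the same way.* The text does not say that dose is reduced to a subject median. A check with per-subject means gave 3-5.5% rejection, and with medians 5-10.5%.

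**Conclusion.** The point holds in a limited form. As specified, the test can reject because subjects on the two regimens bleed at different rates, with no difference in infusions per bleed. At p = 0.65, 4 years and ABR 4.2 against 20.0, false rejection runs from about 50-80% at ICC 0, through 15-30% at 0.05 and 10-15% at 0.1, to 5-10% at 0.2. It is near nominal when p is about 0.5, and also at p = 0.45 once the ICC is 0.05 or more. A smaller gap in bleed rates shrinks it.

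The protocol fixes neither p, the ICC nor the group sizes, so neither the size nor the direction of the error can be predicted for this study. That uncertainty is the reason not to interpret the p-value. It does not show that the planned result will be wrong. The matter is secondary and inexpensive to correct.

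**What to change.** In Section 9.7.3.3, keep the per-subject medians and the planned frequency distribution as description. Remove the Mann-Whitney test on the medians, and show the number of bleeds per subject beside them. For this comparison, that also agrees with the statements in Sections 4, 9.1 and 9.5 that no hypothesis testing is applied.

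If the regimens are to be compared, estimate at bleed level, with the subject as cluster, either the ratio of mean infusions per bleed or the difference in the share of bleeds controlled with one or two infusions. Give a 95% CI and label it exploratory, because the physician chooses the regimen and clustering does not adjust for that.

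Cost: a wording change and no new data. Diary-recorded bleeds and their treatment already go to the e-CRF (Section 9.1), and the diary asks for infusions per bleed (Section 9.4.2). There are two downsides. The bleed-level estimate gives more weight to frequent bleeders and so answers a somewhat different question from a subject-level summary. Robust standard errors are also slightly liberal when one regimen is small, with simulated rejection of about 5-8% at nominal 5%.
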